5.2.2. Immunogenicity Analysis Set (IGS)

The Immunogenicity Analysis Set (IGS) contains all the Anti-Drug Antibody and/or Neutralizing Antibody (ADA/NAb) evaluable patients, who are in the SAF analysis set with at least one ADA/NAb sample (with reportable results) taken pre-treatment (i.e., a baseline sample) and at least one ADA/NAb sample (with reportable result) taken post-treatment in the OLE period.

5.3. Handling of Dropouts or Missing Data

All analyses will be based on observed data; missing data will not be imputed.

5.4. Additional Data Handling Rules and Presentation Specifications

5.4.1. Handling Missing/Incomplete AE Onset Date

If the AE onset date is incomplete or missing, the following rules will be applied to impute AE onset date.

- If year and month are present, only day is missing,
 - a. If AE onset Year/month = Day 1 Year/month, assign onset day = day part of Day 1 (Day 1 is the first infusion day);
 - b. If AE onset Year/month \neq Day 1 Year/month, assign onset day = 1st of the month.
- If year is present, month and day are missing, or when only month is missing (treating day as missing),
 - a. If AE onset year = year of Day 1, assign onset date = month and day part of Day 1 date.
 - b. If AE onset year \neq year of Day 1, assign onset date= January 1st.
- If onset date is completely missing, assign onset date = date of Day 1.

If the stop date is complete and the imputed start date as above is after the stop date, the start date will be imputed by the stop date.

5.4.2. Handling Missing/Incomplete Concomitant Medication Start/Stop Dates

For concomitant medications, including rescue medications, incomplete (i.e., partially missing) start date is imputed the same way as for the AE described above. When the start date and the stop date are both incomplete for a patient, impute the start date first.

Incomplete Stop Date

The following rules are applied to impute the missing stop date, if needed.

- If year is present, month and day are missing, or when only month is missing (treating day as missing)
 - a. If CM stop year = year of last dose, assign stop date = month and day part of of last dose date;
 - b. If CM stop year \neq year of last dose, assign stop date= December 31st.
- If year and month are present, only day is missing,
 - a. If CM stop Year/month = Year/month of last dose date, assign stop day = day part of last dose date
 - b. If CM stop Year/month \neq year of last dose, assign onset day = last day of the month.
- Impute CM end date even if ‘ONGOING’ is checked to report the CM treatment duration in the study if needed.

5.4.3. Definition of Baseline

- Baseline for the OLE period is the acceptable value from the last visit on or before the first dose date in OLE.

- Baseline for main study period is defined the same as in SAP for the main study period.

5.5. Analysis Visit Windows

Efficacy parameters will be summarized by analysis visit defined by the following assessment windows ([Section 15](#)). The date of the first dose will be considered as the date of Day 1 for all analysis. The analysis visit window for some safety assessments such as lab tests and vital signs are also defined in the same section.

5.6. Protocol Deviations

Protocol deviations of interest may include, but are not limited to, the following:

- Subjects who did not meet inclusion/exclusion criteria
- Subjects who received disallowed concomitant medications or non-drug therapy
- Subjects who missed important assessments or did not attend a visit as planned
- Subjects who did not receive adequate dosing.

The number and percentage of important protocol deviations will be categorized and tabulated as appropriate.

6. SUBJECT ACCOUNTABILITY AND DISPOSITION

The number and percentage of subjects who are dosed, completed the treatment or study, and prematurely discontinued will be summarized for the Safety Population.

Reasons for premature discontinuation as recorded on the Study Disposition page of the CRF will be summarized by number and percentage.

All subjects of the Safety Population, including subjects who discontinue prematurely from the study, will be listed with their treatment group, date and time of first and last dose, days in treatment, date of last visit, and reason for discontinuation.

A separate listing for the subjects who discontinue prematurely, date and time of first and last dose, days in treatment, date of last visit, and reason for discontinuation will be presented.

7. DEMOGRAPHICS AND BASELINE CHARACTERISTICS

7.1. Demographics and Baseline Characteristics

Subject demographics, baseline characteristics, baseline disease characteristics, and baseline efficacy measures will be summarized. Baseline disease characteristics include general medical history, disease specific characteristics, and prior treatments. Baseline efficacy measures include PFT parameters, hand and arm functions, cardiac and muscle MRI parameters.

Descriptive statistics (n, mean, standard deviation, median, minimum, and maximum) will be presented for continuous variables. In addition, 25%-75% values of Biomarker will be presented. Frequency distributions (number and percentage of subjects) will be presented for categorical variables.

Descriptive statistics of baseline values for other parameters will be presented in their change from baseline tables.

Demographics and baseline characteristics of the study will be summarized using descriptive statistics.

Demographic variables will include age in years, sex (optional as all DMD subjects are male), race, and ethnicity. Age at baseline is defined as the age when signing informed consent:

$$\text{age} = \text{Year of Date of Informed Consent} - \text{Birth year.}$$

Other baseline characteristics include height, weight, side of dominant hand, BSA, and body mass index (BMI).

Computation formulas:

$$\text{BSA} = [\text{Weight}^{0.425} \text{ (kg)} * \text{Height}^{0.725} \text{ (cm)}] \times 0.007184$$
$$\text{BMI} = \text{Weight (kg)} / (\text{Height (m)})^2$$

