## 1. PROTOCOL SYNOPSIS

Study Title:	Trial of Pamrevlumab (FG-3019), a Monoclonal Antibody to Connective Tissue Growth Factor, in Non-Ambulatory Subjects with Duchenne Muscular Dystrophy
Protocol Number:	FGCL-3019-079, Amendment 8.0
Investigational Product:	Pamrevlumab (FG-3019) (Recombinant fully human IgG1 kappa monoclonal antibody to connective tissue growth factor)
Study Phase:	Phase 2
Target Population:	Non-ambulatory subjects with Duchenne muscular dystrophy (DMD)
Number of Subjects Planned:	Approximately 22 subjects will be enrolled; interim analysis may increase sample size to approximately 32
Study Centers Planned:	Approximately 10 centers

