#### 4.1.3. Exploratory, Pharmacokinetic and Pharmacodynamic Outcome Measures

Exploratory outcome measures for this trial are:

- Pharmacokinetic (PK) profile of pamrevlumab (including Cmin, Cmax, AUCtau, and t1/2) [In the first 12 subjects to have PK/PD samples though Day 14]
  - In the overall population
  - In subjects 12 to 16 years of age, inclusive
  - In subjects older than 16 years
  - Comparison of PK profiles across age groups
- Plasma and urine CTGF
- Creatine kinase (CK)
- Circulating biomarkers
- Exploratory analyses on primary and secondary efficacy endpoints at week 156 will be conducted at the end of the study.

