## 5. STUDY ENROLLMENT AND WITHDRAWAL

### 5.1. Inclusion Criteria

Subjects must meet all of the following criteria in order to be eligible for the study:

1. At least 12 years of age
2. Written consent/assent by patient and/or legal guardian as per regional and/or IRB requirements
3. Non-ambulatory
4. Brooke Score for Arms and Shoulders  $\leq 5$
5. Diagnosis of DMD by medical history and confirmed Duchenne mutation in available genetic testing using a validated genetic test
6. Able to perform spirometry
7. Able to undergo cardiac and extremity (upper arm) MRI
8. Percent predicted FVC between 40 and 90, inclusive
9. At least one historical FVC % predicted value within 18 months of baseline
10. Left ventricular ejection fraction  $\geq 45\%$  as determined by cardiac MRI at screening or within 3 months prior to Day 0
11. Subjects currently receiving heart failure cardiac medications (e.g. angiotensin converting enzyme inhibitors, angiotensin-receptor blockers, and beta-blockers) must achieve a stable regimen for at least 3 months prior to screening
12. On a stable dose of corticosteroids for a minimum of 6 months prior to screening with no substantial change in dosage for a minimum of 3 months (except for adjustments for changes in body weight) prior to screening and no foreseen change in corticosteroid use during the course of study participation
13. Received pneumococcal vaccine and is receiving annual influenza vaccinations
14. Adequate renal function: cystatin C  $\leq 1.4$  mg/L
15. Adequate hematological function:
  - a. Platelets  $>100,000/\text{mcL}$
  - b. Hemoglobin  $>12\text{ g/dL}$
  - c. Absolute neutrophil count  $>1500/\mu\text{L}$
16. Adequate hepatic function:
  - a. No history or evidence of liver disease
  - b. gamma glutamyl transferase (GGT)  $\leq 3 \times$  upper limit of normal (ULN)
  - c. Total bilirubin  $\leq 1.5 \times \text{ULN}$
17. If sexually active, will use medically accepted contraceptives during participation in the study and for 3 months after the last dose of study drug

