9.2.3.1. Analysis Method

The observed and change from baseline in the above efficacy endpoints each will be summarized by analysis visit and analyzed using MMRM with visit, baseline, and age with appropriate covariance matrix for the within subject covariance over time.

If the algorithm for unstructured covariance pattern does not converge, the following covariance structures will be tested in sequence until the model converges: heterogeneous Toeplitz, homogeneous Toeplitz, first-order autoregressive, compound symmetry, and variance component. The sandwich estimator will be used if there is convergence issue. If the model does not converge for all covariance structures listed above, some least significant factors or interaction terms ($p>0.05$) can be excluded from the model to achieve convergence. The revised model with fewer factors or interaction terms will be tested using the same sequence as specified above.

9.2.3.2. Handling of Intercurrent Events:

Treatment discontinuation (such as: due to AEs, Lost to Follow-Up, Withdrawal by subject, Physician Decision, Protocol Deviations, etc.): treatment policy: the occurrence of the intercurrent event is irrelevant. All observed values will be used regardless of whether the inter-current event occurs.

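### SAP 7.1 defines baseline age as age at signing consent but computes a difference of calendar years, which in completed years is either correct or one year too high

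*SAP*

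**What the plan says.** SAP 7.1 (Demographics and Baseline Characteristics) lists age among the demographics: "Demographic variables will include age in years". It does not say whether completed or decimal years are meant. The definition follows: "Age at baseline is defined as the age when signing informed consent". The formula given with it is "Year of Date of Informed Consent" minus the birth year. Neither term uses month or day.

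Age appears once more as an analysis variable. SAP 9.2.3.1 says that change from baseline is "analyzed using MMRM with visit, baseline, and age". That model covers upper limb performance, grip strength, LVEF, the LGE cardiac fibrosis score and global circumferential strain (SAP 9.2.3); SAP 13 also names ppFVC among the parameters for it. No other derivation of age is given in the protocol or the SAP, and nothing marks this one as approximate.

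**The concern.** The definition and the formula are different quantities. Age when signing a form ordinarily means completed years on that day, which requires knowing whether the birthday has passed. A difference of two calendar years assumes that it always has.

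The SAP's other time variables are built from actual dates: exposure duration in 8.1, the elapsed-time variable of the random coefficient model in 9.2.2.1, and patient exposure years in 10.1, which divides by 365.25. Age is the exception.

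At stake are the age reported for the cohort, which readers of a progressive disease use to place it, and the precision of one model covariate.

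**Working it through.** The documents state no figure for this point, so there is none to reproduce. The check works from the definition and formula in SAP 7.1.

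**Hypothetical records**

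| Born | Consent | Formula | Completed years | Exact age | Formula minus exact |
|---|---|---|---|---|---|
| 20 Dec 2003 | 10 Jan 2016 | 2016 - 2003 = 13 | 12 | 12.06 | +0.94 |
| 5 Jan 2003 | 20 Dec 2016 | 2016 - 2003 = 13 | 13 | 13.96 | -0.96 |

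**Against completed years.** Let b be the birthday and c the consent date, each as a position within the calendar year. The formula minus completed age is 1 if b falls after c, and 0 otherwise. It is never negative.

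- Assumption: birthdays and consent dates are independent and uniform over the year. The documents give no dates.
- Counting all 365 × 365 pairs, b falls after c in 0.4986 of them, or 49.9%. The mean overstatement is therefore about 0.5 year.
- The protocol synopsis says "Approximately 22 subjects will be enrolled". Taking 22 as an illustration, 22 × 0.5 = 11 subjects are expected to be affected, with a 95% binomial range of 6 to 16. The number who entered the extension is not stated.

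**Sensitivity to timing of consent** (birthdays still uniform, all consents in one quarter)

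| Quarter of consent | Share one year too high |
|---|---|
| Q1 | 87.5% |
| Q2 | 62.7% |
| Q3 | 37.7% |
| Q4 | 12.5% |

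**Against exact decimal age.** Exact age equals the year difference plus (c - b), so the error of the formula is b - c.

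- Mean: 0.
- SD: √(1/12 + 1/12) = √(1/6) = 0.41 year.
- Range: -1 to +1 year.
- Share with an absolute error above half a year: 25%.

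**If only birth year is held.** Counting from 1 July of the birth year leaves the distance between the birthday and 1 July as the error. It runs from -0.5 to +0.5 year, with SD 1/√12 = 0.29 year. Rounding this down would still misstate completed age in 12.5% + 12.5% = 25% of subjects, so it should stay unrounded.

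**Where the variable enters.** The random coefficient model in SAP 9.2.2.1 has time and the baseline value as fixed effects. The natural-history comparison in 9.2.4 adds treatment and its interaction with time. The code in Appendix 2 agrees. None of these contains age; only the MMRM does.

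**The case against.** The strongest defence has three parts.

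1. The SAP asks for age in years, not completed years. Against exact age the formula has mean error 0, and it is rounded-down age that runs about half a year low on average. This stands: the upward error exists only on the completed-years scale. A reader might infer that the cohort is made to look older than it was. That cannot be said without naming the scale.
2. The effect on analysis is close to nil. In this single-arm MMRM a constant shift in age is absorbed by the intercept and leaves visit means at mean age unchanged. This also stands: only covariate noise remains.
3. The formula may reflect the data held, if only birth year is recorded. The documents do not settle this. If it is so, the SAP should call the variable approximate instead of equating it with age at signing.

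Other stronger readings are tempting but not supported:

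- **Pharmacokinetic age groups.** A reader might infer that 16-year-olds are moved out of the group described in Protocol 4.1.3 as "In subjects 12 to 16 years of age, inclusive". Those groups belong to the main-study pharmacokinetic analysis (Protocol 9.4.6). This formula stands in the extension SAP, which has no pharmacokinetic analysis and no age subgroup. The main-study SAP of June 2020, cited in the SAP addendum, is not among the documents, so its age derivation is unknown.
- **Eligibility and percent predicted FVC.** The protocol's entry limit ("At least 12 years of age") and the calculation of percent predicted FVC are nowhere tied to this variable.
- **Natural-history comparison.** The specified model has no age term. Any later matching on prognostic factors is left to a separate SAP (SAP 9.2).

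None of this reconciles the definition with the formula.

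**Conclusion.** The point holds as a mismatch between a definition and its derivation, and it is minor. Followed literally, SAP 7.1 gives a completed age one year too high for every subject whose birthday falls after the consent date in that calendar year. The one-half share rests on evenly spread birthdays and consent dates, and seasonal enrolment could move it widely. On the decimal scale the fault is imprecision, not bias.

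The consequence is confined to the age line of the demographics table and slight noise in the MMRM covariate. The SAP also does not say whether the main-study or the extension consent is meant. That is a separate ambiguity, and nothing here depends on it.

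**What to change.** Replace the formula in SAP 7.1 with age = (date of informed consent - date of birth)/365.25. Round it down to completed years for the demographics table, and use it unrounded as the MMRM covariate.

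One programming detail: division by 365.25 can fall just short on a birthday. Thirteen years containing three leap days is 4748 days, and 4748/365.25 = 12.9993. A function that compares month and day avoids this in the rounded version.

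If only birth year is held, use (consent date - 1 July of birth year)/365.25, unrounded, and label it approximate in the SAP and the table. On the decimal scale this reduces the error SD from about 0.41 to about 0.29 year.

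The cost is one line of SAP text and one derived variable. No new data are needed in either case.

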7.2. Medical History

Medical history, including allergies and surgeries, will be tabulated in system organ class (SOC) and preferred term (PT) using MedDRA version 26.0 or higher.

8. TREATMENTS AND MEDICATIONS

8.1. Study Drug Exposure

The number and percentage of subjects who receive study medication will be summarized.

Duration in weeks from first infusion to last infusion, calculated as (last dose date – first dose date+1)/7, will be summarized by the categories as follows:

<= 26 weeks
>26 weeks to <=52 weeks
>52 weeks to <=78 weeks
>78 weeks to <=104 weeks
>104 weeks to <=156 weeks
>156 weeks to <=208 weeks
>208 weeks

The number of infusions and average infusion dose amount in mg and mg/kg, any interruption during infusion (Y/N), and reason for missed dose or interruption will be summarized.

The compliance will be presented as % of actual doses of infusion administered out of the expected total dose of infusions during study. Compliance = (actual doses received / expected doses during study) * 100%. Treatment compliance will be summarized as a continuous variable and as a categorical variable (<70%, 70% -<80%, 80% - 90%, and >90%).

Duration of exposure, weekly exposure and total study drug exposure will be tabulated.

8.2. Concomitant Medications

The historical use of the medications is summarized using descriptive statistics for the Safety population.

Medications recorded on the Concomitant Medication CRF are classified in the analysis dataset in the following categories:

- Concomitant medications - medications that are used concomitantly with the study drug, which are defined as medications that were not stopped before the first infusion.
- Use of corticosteroids

Concomitant medications are summarized by ATC class and preferred term. Subjects reporting more than one use of the same medication will be counted only once in the summary tables.

All medications captured in Concomitant Medication CRF, as well as Non-Drug Therapies CRF are presented in data listings.

9. EFFICACY ANALYSIS

9.1. Efficacy Endpoints

The Efficacy Endpoints are:

Pulmonary assessment:

- Annual mean change in percent predicted forced vital capacity (ppFVC%) assessed by spirometry.

Performance assessments:

- Annual mean change from baseline in the total score of Performance of Upper Limb (PUL).
- Annual mean change from baseline the Grip strength of the hands extremities assessed by Hand Held Myometry (HJM).

Cardiac assessments:

- Annual mean change from baseline in cardiac fibrosis score assessed by Late Gadolinium Enhancement (LGE).
- Annual mean change from baseline in Left Ventricular Ejection Fraction percentage (LVEF %) assessed by MRI.
- Annual mean change from baseline in Myocardial Circumferential Strain [Mean Peak Circumferential strain (MPCS) and Global Circumferential Strain (GCS) percentage] assessed by cardiac MRI.

In addition to the analysis of annual mean changes of the above efficacy endpoints with random coefficient model (RCM), the change from baseline in the following efficacy endpoints of PUL, grip strength, LVEF%, and cardiac MRIs including cardiac fibrosis score assessed by Late Gadolinium Enhancement (LGE), and Myocardial Circumferential Strain [Global Circumferential Strain (GCS)], will be analyzed with Mixed Model for Repeated Measures (MMRM) at Week 48/52, Week 96/104, Week 144/156, and Week 192/208 per the schedule, without assuming linear trajectories by disease progression.

9.2. Analysis Methods for Efficacy Endpoints

Unless otherwise noted, long-term treatment effects of all efficacy endpoints at each timepoint will be summarized and analyzed from the baseline of the main study through the last visit in the extension phase. Change from baseline values in efficacy endpoints will be analyzed with MMRM Annual rate of change from baseline using Random Coefficient Model (RCM) analysis, and the estimated change from baseline values at year 1 through year 4 described in the following sub-sections will be presented.

The sponsor will conduct an exploratory comparison of disease progression of FGCL-3019-079 clinical trial participants with natural history data of patients with non-ambulatory DMD. If

warranted, analyses adjusting for matching on established baseline prognostic factors will be conducted under a separate SAP.

9.2.1. Descriptive Summary

Continuous variables will be presented by descriptive statistics: n, mean, standard deviation (SD), standard error (SE), median, 25th and 75th percentile, minimum, and maximum. The 2- sided 95% confidence interval for the mean and median will be presented as appropriate.

Categorical variables will be tabulated by frequency count and percentage. The confidence interval for the proportions for each will be calculated using the Clopper-Pearson method as appropriate.

9.2.2. Annual Change from Baseline to Week 208 in Efficacy Endpoints with RCM

The following endpoints will be analyzed with the same RCM analysis method.

1. Annual mean change from baseline in the Percent Predicted FVC (ppFVC)
2. Annual mean change from baseline in the total score of Performance of Upper Limb (PUL)
3. Annual mean change from baseline the Grip strength of the hands extremities assessed by Hand Held Myometry (HHM)
4. Annual mean change from baseline in cardiac fibrosis score assessed by Late Gadolinium Enhancement (LGE)
5. Annual mean change from baseline in Left Ventricular Ejection Fraction percentage (LVEF %) assessed by MRI
6. Annual mean change from baseline in Myocardial Circumferential Strain [Mean Peak Circumferential strain (MPCS) and Global Circumferential Strain (GCS) percentage] assessed by cardiac MRI

9.2.2.1. Analysis Method

Annual mean change from baseline in the above efficacy endpoints each will be analyzed using Random Coefficient Model (RCM) analysis, and the estimated annual change from baseline values at year 1 through year 4 in the OLE period will be presented.

The model will include continuous variable avisityr (calculated as the elapsed days of assessment date from baseline date in the unit of year) and baseline endpoint as fixed effects, while the intercept and avisityr are included as random effects.

The unstructured covariance structure for the within-patient errors in the model will be applied first. The by-treatment-group option is included to the covariance pattern to improve the model efficiency.

If the algorithm for unstructured covariance pattern does not converge, the following covariance structures will be tested in sequence until the model converges: heterogeneous Toeplitz, homogeneous Toeplitz, first-order autoregressive, compound symmetry, and variance component. The sandwich estimator will be used if there is convergence issue. If the model does not converge for all covariance structures listed above, some least significant factors or interaction terms ($p>0.05$)

can be excluded from the model to achieve convergence. The revised model with fewer factors or interaction terms will be tested using the same sequence as specified above.

When the random effects model does not converge or do not have a positive definite Hessian, the fixed effects instead of random effects for the intercept and slope will be performed instead.

The LSMean (SE) and 95% CI for annual change (slope) as well as estimated changes from baseline at year-1, year 2, year 3 and year 4 (regarding week 52, week 104, week 156 and week 208) will be presented.

9.2.2.2. Handling of Intercurrent Events:

Treatment discontinuation (such as: due to AEs, Lost to Follow-Up, Withdrawal by subject, Physician Decision, Protocol Deviations, etc.): treatment policy: the occurrence of the intercurrent event is irrelevant. All observed values will be used regardless of whether or not the inter-current event occurs.

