9.2.4. Exploratory Analysis - Comparison with the CINRG natural history data

Efficacy endpoints: % predicted FCV (ppFVC), LVEF, and grip strength in dominant hand will be compared with a subset of CINRG DMD Natural History study (DNHS) data with all 36 subjects using a random coefficient model (RCM). The other outcome measures including Performance of Upper Limb (PUL), cardiac fibrosis by LGE, and Myocardial Circumferential Strain [Mean Peak Circumferential strain (MPCS) and Global Circumferential Strain (GCS) percentage] assessed by cardiac MRI are not available in CINRG data and therefore will not be compared.. The RCM model will use efficacy data from both the main and OLE periods and include continuous variable avisityr (calculated as the elapsed days of assessment date from main study baseline date in the unit of year), treatment trt (079 subjects as treated with trt = 1, and subjects in CINRG data as control with trt =0), the interaction term of trt and avisityr, and baseline endpoint as fixed effects, while the intercept and avisityr are included as random effects. The strategy for covariance structure for the within-patient errors in the model is the same as what is described in [Section 9.2.2.1](#). The LSMean (SE) for annual change (slope) as well as LSMean (SE) and 95% CI of treatment differences between pamrevlumab and control of estimated changes from baseline at year 1, year 2, year 3 and year 4 in the OLE period will be presented. The sample SAS code is provided in [Appendix 2](#).

Line plots of each subject's efficacy trajectory compared with the mean plot of the CINRG will be provided.

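### The convergence rule in SAP 9.2.2.1 and 9.2.3.1 lets fixed effects be dropped on p>0.05 and does not protect the terms that define the estimand or the baseline adjustment

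*SAP*

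**What the plan says.** SAP 9.2.2.1 gives the convergence steps for the RCM. They start from an unstructured covariance and move through five simpler structures, with a sandwich estimator if convergence is a problem. If every structure fails, "some least significant factors or interaction terms" with p>0.05 may be left out. Then: "The revised model with fewer factors or interaction terms will be tested using the same sequence as specified above". A separate sentence allows fixed instead of random intercept and slope when the random-effects model fails. SAP 9.2.3.1 repeats the structure sequence and the term-dropping sentences for the MMRM.

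The fixed effects are few. For the RCM: "The model will include continuous variable avisityr", together with "baseline endpoint as fixed effects, while the intercept and avisityr are included as random effects". The MMRM has visit, baseline and age. The comparison with the CINRG natural history data in 9.2.4 has avisityr, trt, "the interaction term of trt and avisityr, and baseline endpoint as fixed effects".

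Section 9.2.4 points back to 9.2.2.1 in these words: "The strategy for covariance structure for the within-patient errors in the model is the same as what is described in". For the RCM, the required output is: "The LSMean (SE) and 95% CI for annual change (slope) as well as estimated changes from baseline at year-1, year 2, year 3". That sentence goes on to include the fourth year. Section 9.2.4 asks for annual slopes and for treatment differences at each of years 1 to 4.

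**The concern.** A rule for numerical trouble should not be able to remove the quantity the model exists to estimate. Here any fixed effect with p>0.05 is a candidate, and each model contains at least one term without which the required output does not exist.

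There are three further problems.

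- The p-value would come from a fit that did not converge. Its standard errors rest on covariance estimates that the algorithm never settled on, so the test is not valid. The rule does not say which of the failed fits supplies the p-value, or how many terms may go.
- All the preceding steps simplify the covariance. Deleting a mean term does not address that part of the model.
- The order of term deletion and the fixed-effects fallback in 9.2.2.1 is not stated. Two analysts could follow the SAP and report different models.

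At stake are the slope and the visit-specific changes in the single-arm analyses, the pre-specified baseline adjustment, and, if the rule reaches 9.2.4, the slope difference in the only between-group comparison. Selection of this kind would remove the slope difference precisely when it was not significant.

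**Working it through.** The plan states no figure that depends on this rule, so there is none to reproduce. The check has two parts.

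**1. Terms the rule could remove**

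| Model | Fixed effects | Carry the estimand | If removed |
|---|---|---|---|
| RCM (9.2.2.1) | avisityr, baseline | avisityr: 1 of 2 | no slope; year 1 to 4 estimates identical |
| MMRM (9.2.3.1) | visit, baseline, age | visit: 1 of 3 | no visit-specific change |
| CINRG RCM (9.2.4, Appendix 2) | trt, avisityr, trt by avisityr, baseline | first three: 3 of 4 | without the interaction, same difference at years 1, 2, 3 and 4 |

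In total 1 + 1 + 3 = 5 of 2 + 3 + 4 = 9 terms carry the estimand. The other four are covariates: baseline three times and age once.

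Does the rule reach 9.2.4? The link there is worded for covariance strategy only. Two features of 9.2.2.1 point to the wider reading. It speaks of interaction terms, but neither single-arm model has one; trt by avisityr is the only interaction in the three models. It also calls for a covariance pattern that varies by treatment group. That means nothing with one arm and matches only the two-group sample code in Appendix 2.

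**2. Illustration for the CINRG model**

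Assumed inputs, not given in the documents for this analysis:

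- 21 treated subjects
- 36 controls (9.2.4 mentions 36 subjects, but the wording is ambiguous)
- eight half-yearly visits, t = 0.5 to 4 years
- true slope difference d = 2 points per year, so 2 × 4 = 8 points at year 4
- slope SD τ from 1 to 5 and residual SD σ from 3 to 5
- random intercept and slope independent, covariance known

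The visit times have mean 2.25 and sum of squared deviations S = 10.5.

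Standard error of the interaction: SE = √[(τ² + σ²/S)(1/21 + 1/36)].

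Chance of p>0.05: Φ(1.96 − d/SE) − Φ(−1.96 − d/SE).

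Expected constant difference when the interaction is left out: d × 2.25 × (σ²/S)/(τ² + σ²/S).

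Worked case τ = 3, σ = 3: σ²/S = 9/10.5 = 0.857. SE = √(9.857 × 0.0754) = 0.86. The chance of p>0.05 is 36%. The constant is 4.5 × 0.857/9.857 = 0.39.

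| τ | σ | SE | P(p>0.05) | Constant reported |
|---|---|---|---|---|
| 1 | 3 | 0.37 | about 0% | 2.1 |
| 1 | 5 | 0.50 | 2% | 3.2 |
| 2 | 3 | 0.61 | 9% | 0.8 |
| 3 | 3 | 0.86 | 36% | 0.39 |
| 5 | 3 | 1.40 | 70% | 0.15 |
| 5 | 5 | 1.44 | 71% | 0.39 |

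If the working covariance has no random slope, the last factor in the constant becomes 1 and the constant is 2 × 2.25 = 4.5. In every case it replaces true differences of 2, 4, 6 and 8 points at years 1 to 4.

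**The case against.** The case on the other side is substantial.

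- Term deletion is a last resort. The unstructured covariance and five simpler structures must all fail first. The wording is permissive, and the RCM has another fallback that simplifies the random effects.
- The required outputs count against deleting the target. Slopes and yearly changes are to be presented, and a model without avisityr cannot give a slope. A marked decline over time is also unlikely to have p>0.05.
- Section 9.2.4 takes over only the covariance strategy and names its fixed effects, and the Appendix 2 code includes them.
- The CINRG comparison is exploratory. The protocol (Appendix 6, section 5) asks only for descriptive summaries of the extension.

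All of this limits the consequence. It does not cure the rule. The protection from the required outputs is implicit only and does not cover baseline. The text exempts nothing, and the order of the two fallbacks remains open.

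A reader might infer that almost every term in these models is the effect being estimated. The count does not support that: it is 5 of 9 overall, and only the CINRG model fits the description. A reader might also infer that the SAP expressly applies term deletion to the CINRG comparison. It does not; that reach is inferred from a reference about covariance and from two phrases that suit only a two-group model.

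**Conclusion.** The point stands as a defect in a stated rule. SAP 9.2.2.1 and 9.2.3.1 permit removal of avisityr, visit or baseline on an invalid p-value, and the rule can reasonably be read to cover trt by avisityr in 9.2.4.

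The size cannot be fixed from the documents. Under the assumed inputs, a real slope difference of 2 points per year has p>0.05 in about 0% to 71% of trials. The constant reported in its place is about 0.15 to 3.2 points, or about 4.5 with no random slope, against a true 8 points at year 4. It would be tempting to read a single pair, such as 36% and 0.39 points, as the expected harm. That is not supported. The result depends heavily on the assumed slope SD and on the working covariance. The percentages are also not conditional on convergence failure, whose frequency the documents do not allow one to estimate.

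The practical impact is limited. No sample size, power or main-study decision rule changes. The correction is still worth making because the fault is explicit, occurs twice and is easily removed.

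**What to change.** Delete the term-dropping sentences, including the sentence on refitting the reduced model, in SAP 9.2.2.1 and 9.2.3.1. State in their place:

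- avisityr (RCM), visit (MMRM), trt and trt by avisityr (CINRG comparison) and baseline are always kept. As no fixed effect may then be deleted, age also stays in the MMRM.
- Only the covariance or random-effects structure may be simplified, in the listed order. For the RCM, the existing change from random to fixed intercept and slope is the last step. The MMRM has no random effects, so its sequence ends with the simplest covariance structure.
- The same rule applies to 9.2.4.

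The cost is a few sentences of SAP text. It needs no new data and changes no sample size, power or significance level.
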